## **Randomization/Blinding**

Participants will be randomly assigned following simple envelope randomization procedures to one of the two treatment groups. Patients will be blinded from the treatment group, and the examinations will be performed by a blinded examiner.

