## **Methods**

The study will employ a double-blind randomized controlled study design. Ethical approval has been obtained from Kuwait Ministry of Health, Ethics committee. Written informed consent will be completed. Seventy patients both Kuwaitis and non-Kuwaitis with frozen shoulder attending the outpatient department of the Al Farwaniya hospital and PM& R hospital will be randomly assigned to the heavy slow resistance exercises group and the control group.

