## **Sample size**

Shoulder external rotation range of motion is considered as the primary outcome measure for the proposed study. A study by Celik (2010) [24] was used to inform the sample size calculation, where the shoulder external rotation was measured at baseline and at 12-week post intervention for the glenohumeral range of motion exercise group. Using the means and standard deviations of 22 (12.5) degrees and 33 (14.9) degrees for external rotation range of motion changes resulted in an effect size of -0.799. With a two tailed hypothesis, the minimum required sample size is 30 patients per group at ( $\alpha$ ) 0.05 and a power (1-  $\beta$ ) of 85%. 35 participants per group will be recruited to account for attrition.

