## **Intervention**

Both groups will receive conventional therapy sessions which include active ROM exercise, strengthening and stretching exercises, end-range mobilization and hot packs (if indicated). Exercises will be given within the pain threshold limit twice a week for 12 weeks. In addition, the experimental group will receive heavy slow resistance exercise program using a theratube. The exact management approach will be standardized between the two groups in terms of intensity and frequency and the experimental group will only receive additional heavy slow resistance exercise.

Subjects will be assessed at baseline and at 3, 6, and 12 months. Shoulder external rotation and abduction ROM will be measured and compared within and between groups and will be analyzed using a One-way ANOVA.

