**Data analysis**

SPSS will be used for statistical analysis. All outcome measures will be analyzed using one-way ANOVA.

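### Two hospitals recruit, but the stated one-way ANOVA has no hospital term: the plan is valid, and adding the term is a near-free gain in precision if the hospitals differ

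*Protocol*

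**What the plan says.** Under Methods, the 70 patients are those "attending the outpatient department of the Al Farwaniya hospital and PM& R hospital", so there are two recruiting hospitals. Under Randomization/Blinding, "Participants will be randomly assigned following simple envelope randomization procedures to one of the two treatment groups". No strata are stated, and hospital is not mentioned. The model is named twice. Under Intervention, the range-of-motion measures "will be measured and compared within and between groups and will be analyzed using a One-way ANOVA"; under Data analysis, "All outcome measures will be analyzed using one-way ANOVA". A one-way ANOVA has one factor, so a between-group comparison on this text contains treatment and nothing else. Hospital appears nowhere in the allocation or the analysis.

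The planning figures are under Sample size: "Using the means and standard deviations of 22 (12.5) degrees and 33 (14.9) degrees for external rotation range of motion changes", which "resulted in an effect size of -0.799", leading to 30 per group for 85% power at two-sided 0.05, with 35 recruited to allow for attrition.

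**The concern.** Treatment is hands-on therapy given over 12 weeks at two hospitals, so some difference in outcome between hospitals is plausible, though the protocol documents none. If there is one, two things follow.

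- A plain one-way ANOVA counts the hospital difference as residual noise, so the treatment comparison is less precise than it could be.
- Nothing stated keeps the hospital mix alike in the two arms. With one shuffled set of 35 + 35 envelopes, the chance that the mix differs by 20 percentage points or more is 15.1%, 8.7% or 11.7% for assumed hospital splits of 35/35, 28/42 or 21/49. With unrestricted draws it is 12.0%, 9.2% or 7.5%.

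Precision is at stake, not validity. The margin at 30 per arm is about one point of power (86.1% against a target of 85%), so a cheap gain is worth taking. Because the protocol itself names the model for every outcome, this is a comment on a stated method and not on a detail left for later.

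**Working it through.** **Inputs.** From Sample size: means 22 and 33 degrees, SDs 12.5 and 14.9, two-sided alpha 0.05, 30 per group needed, 35 recruited. Assumed, because the documents do not give them: equal hospitals, and a hospital difference h of 0, 5 or 11 degrees. The last equals the planned treatment effect and is extreme.

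**1. The plan's own figure.** Pooled SD = √((12.5² + 14.9²)/2) = √189.13 = 13.75. Effect size = 11/13.75 = 0.80, which matches the stated 0.799 in size. With the noncentral t distribution, power is 84.9% at 29 per arm and 86.1% at 30. The stated 30 is therefore the smallest number that reaches 85%.

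**2. Power with and without a hospital term, 30 per arm.** The noncentrality is (11/SD) × √(30/2), with 58 residual degrees of freedom without the term and 57 with it. The documents do not say whether 13.75 includes variation between hospitals, so both readings are shown. With equal hospitals, a difference h adds h²/4 to the variance.

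*Reading A: 13.75 is the within-hospital SD.* Without the term the error SD is √(189.13 + h²/4); with the term it is 13.75.

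| h (degrees) | SD without term | Power without | Power with |
|---|---|---|---|
| 0 | 13.75 | 86.1% | 86.1% |
| 5 | 13.98 | 85.0% | 86.1% |
| 11 | 14.81 | 80.7% | 86.1% |

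*Reading B: 13.75 is the total SD.* Without the term the error SD is 13.75; with the term it is √(189.13 − h²/4).

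| h (degrees) | SD with term | Power without | Power with |
|---|---|---|---|
| 0 | 13.75 | 86.1% | 86.1% |
| 5 | 13.52 | 86.1% | 87.2% |
| 11 | 12.60 | 86.1% | 91.3% |

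**3. The same with all 35 per arm evaluable.** On reading A without the term, power is 91.0%, 90.1% and 86.5% for h = 0, 5 and 11. On reading B without the term it is 91.0% throughout. The plan as written stays above 85% in every case.

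**4. Cost of the term.** At h = 0 and 30 per arm, power goes from 86.13% to 86.11%, a loss of 0.02 points. This assumes that hospital is balanced between arms. The next step shows the cost when it is not.

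**5. Simulation of the whole procedure.** 60 evaluable patients, equal hospitals, total SD fixed (reading B), 8,000 runs per cell. Simple allocation here means independent draws. 0.8 SD is 0.8 × 13.75 = 11 degrees.

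| Hospital difference | Simple, no term | Simple, with term | Stratified, with term |
|---|---|---|---|
| 0 | 85.7% | 85.1% | 86.1% |
| 0.5 SD | 85.7% | 87.1% | 88.5% |
| 0.8 SD | 85.4% | 90.5% | 91.6% |

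At 0.8 SD the term alone gives 90.5 − 85.4 = 5.1 of the 91.6 − 85.4 = 6.2 points available. With no hospital difference, chance imbalance makes the term cost about half a point (85.7% to 85.1%) under unstratified draws.

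**6. Type I error.** Simple allocation with the plain ANOVA stays at about 5% for every hospital difference tried. Stratifying by hospital while keeping the plain ANOVA makes the test conservative: 4.3% at 0.5 SD and 3.2% at 0.8 SD. Adding the term restores about 5%.

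**7. Predictability.** Suppose someone sees past assignments and always guesses the arm that is behind. The expected share of correct guesses is 50% with unrestricted draws, about 57% with one shuffled 35 + 35 set, about 58% with a shuffled set for a hospital of 35, and about 69% with permuted blocks of 4 and 6.

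**The case against.** The strongest reply is that nothing here is an error. Simple randomization with an unadjusted comparison is a legitimate design, its type I error is right, and the hospital difference that would make adjustment worthwhile is assumed. That stands, and it is why the point is a minor improvement.

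A second reply is that the wording on envelopes would also fit a separate shuffled set at each hospital, in which case the imbalance figures do not apply. That also stands. It does not help the analysis, because balance without the term makes the plain ANOVA conservative when hospitals differ.

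A third is that a statistical analysis plan, not shown, could add the term. It could, but it would then depart from the single-factor model that the protocol names for all outcomes.

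A fourth is that stratified allocation has a price of its own. For small permuted blocks this is correct: the therapists who deliver the added exercise know the allocation, and blocks of 4 and 6 raise correct guessing to about 69% for anyone who sees past assignments. The model term carries no such risk, and one shuffled set per hospital adds about one point (58% against 57%).

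A reader might go further and infer that the trial is underpowered or biased. The documents do not support that. On reading A power is still 85.0% at 5 degrees. It falls below target only for a larger difference with nearly all of the ten spare patients lost. On reading B the plan keeps its 86.1% and only an optional gain is forgone.

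**Conclusion.** The point holds as a minor design improvement. The allocation states no hospital stratification and the named model has no hospital term. The scheme is valid and unbiased, and no loss is demonstrable from the documents. What the plan forgoes is precision, and only if the hospitals differ. At 30 per arm that is about 1 power point for a 5-degree difference and about 5 points for an extreme 11-degree difference, on either reading of the planning SD.

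These sizes rest on assumed hospital differences, equal hospitals, and a planning SD taken from baseline and 12-week values of one group in a cited study. They show the scale of the effect and should not be read to a tenth of a point.

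A reader might also infer that small stratified blocks are required. They are not: the model term alone gives most of the gain.

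**What to change.** Add hospital as a factor to the between-group model for all outcomes, so that the stated one-way ANOVA becomes a model with treatment and hospital. This costs one residual degree of freedom: 0.02 power points at 30 per arm when hospital is balanced between arms, and about half a point on average under unstratified draws if hospitals do not differ at all. It needs no extra patients or visits.

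Optionally, prepare a separate shuffled envelope set with equal arms for each hospital and say so under Randomization/Blinding. This balances hospital between arms and removes most of that half point. It requires a planned number of patients per hospital before enrolment, and the balance is only approximate if a set is not used up. If it is done, the hospital term must stay in the model, because stratified allocation with a plain one-way ANOVA is conservative when hospitals differ.

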## **Objective**

The objective of this study is to compare the effect of heavy slow resistance exercises with conventional physical therapy alone for the management of frozen shoulder using double-blind randomized controlled trial design.

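### The protocol calls the trial double-blind with patients blinded, but patients cannot be blind to an added exercise programme that they perform themselves; the design clearly supports only a blinded examiner

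*Protocol*

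**What the plan says.** Three sections of the protocol make the blinding claim:

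- **Objective** sets the new programme against "conventional physical therapy alone for the management of frozen shoulder using double-blind randomized controlled trial design".
- The same label is repeated under **Methods**, which states: "The study will employ a double-blind randomized controlled study design".
- **Randomization/Blinding** names the two blinded parties: "Patients will be blinded from the treatment group, and the examinations will be performed by a blinded examiner".

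The Intervention section describes what patients do. For the common part, "Both groups will receive conventional therapy sessions which include active ROM exercise, strengthening and stretching exercises", together with mobilization and, if indicated, hot packs. For the difference between arms, "In addition, the experimental group will receive heavy slow resistance exercise program using a theratube". The section then confirms that this is the whole contrast: "the experimental group will only receive additional heavy slow resistance exercise".

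Outcome Measures lists active and passive abduction and active and passive external rotation as primary. QuickDASH, pain on a VAS, SF-12 and the Oxford Shoulder Score (OSS) are secondary.

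**The concern.** The treatment contrast is physical work that the patient does with a piece of equipment. A patient knows whether they perform it, and a control patient has nothing in its place. The protocol nevertheless says that patients are blinded and calls the trial double-blind without qualification.

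The consequence lies in interpretation. A reader who accepts the label will assume that expectation is balanced between the arms and will trust the pain and function results accordingly. A blinded examiner cannot provide that balance when the patient supplies the score. The examiner's blind is also the one the design can clearly sustain, and a patient who mentions their exercises at an assessment would break it.

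**Working it through.** No formula applies to the blinding claim. The check compares what is claimed with what is described, then counts the outcomes affected.

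**Step 1. Claim against design**

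| Question | What the protocol states | Where |
|---|---|---|
| Who is blinded? | Patients and the examiner | Randomization/Blinding |
| What is the label? | Double-blind | Objective; Methods |
| What do both arms receive? | Conventional therapy, which already includes strengthening | Intervention |
| What does only one arm receive? | A theratube resistance programme performed by the patient | Intervention |
| What replaces it in the control arm? | Nothing; the comparator is conventional therapy alone | Objective; Intervention |
| How are patients masked? | No method described | – |

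The first two rows require that patients cannot tell their treatment. The fourth and fifth rows describe a difference that patients can see and feel. Both sets of statements cannot hold if blinding means blinding to the treatment received.

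**Step 2. Which outcomes are exposed (from Outcome Measures)**

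- Primary: {active, passive} × {abduction, external rotation} = 2 × 2 = 4 measures. Patient-reported: 0/4 = 0%. Active, so dependent on patient effort: 2/4 = 50%. Passive: 2/4 = 50%.
- Secondary: QuickDASH + VAS + SF-12 + OSS = 4 measures. Patient-reported: 4/4 = 100%.

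The Sample size section names external rotation alone as primary and does not say whether active or passive. On that narrower reading the primary is one or both of two measures (active and passive external rotation), of which one is active. None is patient-reported on either reading, so the conclusion is the same.

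**Step 3. Is the sample size touched?**

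The means and standard deviations in Sample size give a pooled SD of √((12.5² + 14.9²)/2) = 13.75 and d = (33 − 22)/13.75 = 0.80 (stated as −0.799). At two-sided α = 0.05 and 85% power, the t-test needs 29.1, rounded up to 30 per group, which agrees with the protocol. Blinding status does not enter this calculation, so the sample size is unaffected.

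**The case against.** The strongest reply is that the protocol says patients are blinded to the group, not to the exercises. Both arms do strengthening work, so a patient handed a theratube need not know that it marks the experimental arm. How patients are kept unaware would normally be explained in the consent form. The Methods section says "Written informed consent will be completed", but the form is not in the copy reviewed, so its silence cannot be held against the plan.

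This stands in part. Masking of the hypothesis or of the arm label is possible, and the sentence in Randomization/Blinding can be read that way. But that is weaker than blinding to treatment, and an unexplained double-blind label does not convey it. No consent wording could hide from patients the exercises they do. The finding rests on what the protocol asserts against what it describes, not on the missing form.

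A second reply is that the consequences are limited, because the primary outcome is measured by a blinded examiner. This is correct, and it is why the point concerns labelling and interpretation rather than the viability of the trial.

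A third is that the active/passive split is too neat. The protocol's own background reports that passive motion increased under anaesthesia in five patients and attributes restriction partly to fear and muscle guarding. On that account, passive motion in an awake patient may also depend on the patient. That is a fair criticism of the count, but it means that two of four may understate the exposure; it does not weaken the concern.

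**Conclusion.** The concern holds. As described, the trial is not double-blind in the sense that patients are unaware of their treatment; the blind it clearly supports is the examiner's. All four secondary outcomes lack protection from patient expectation, and at least the two active measures among the four listed as primary depend on effort. Range of motion keeps the protection of a blinded examiner.

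These counts show where the label misleads. The protocol gives no information from which to estimate the size of any bias, and none is claimed here.

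The conclusion assumes that the Intervention section is complete, so that controls have no matched extra activity. It does not depend on what the consent form says: that could establish masking of the hypothesis or arm label, but not of the exercises.

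**What to change.** 1. In Objective and Methods, replace double-blind with assessor-blinded.
2. In Randomization/Blinding, state that the examiner is blinded and that patients are not blinded to the exercises they receive. If patients are kept unaware of the hypothesis or of which arm is experimental, say exactly that and how it is done, for example what the consent form tells them about the two arms.
3. Add a sentence on interpretation: QuickDASH, VAS, SF-12 and OSS are not protected by blinding to treatment, and active range of motion depends on effort.
4. Ask patients not to tell the examiner which exercises they do.

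The cost is wording in three sections, one sentence on interpretation and one instruction to patients, with no extra staff, visits or procedures. The Methods section records that "Ethical approval has been obtained from Kuwait Ministry of Health, Ethics committee", so a minor amendment may be needed; the protocol does not say. The downside for the sponsor is a less favourable design label and weaker claims for pain and function.

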## **Intervention**

Both groups will receive conventional therapy sessions which include active ROM exercise, strengthening and stretching exercises, end-range mobilization and hot packs (if indicated). Exercises will be given within the pain threshold limit twice a week for 12 weeks. In addition, the experimental group will receive heavy slow resistance exercise program using a theratube. The exact management approach will be standardized between the two groups in terms of intensity and frequency and the experimental group will only receive additional heavy slow resistance exercise.

Subjects will be assessed at baseline and at 3, 6, and 12 months. Shoulder external rotation and abduction ROM will be measured and compared within and between groups and will be analyzed using a One-way ANOVA.

## **Inclusion Criteria**

Inclusion criteria are males and females, Kuwaiti and non-Kuwaiti between 40 and 65 years with unilateral painful, restricted active and passive range of motion of the shoulder, with loss of passive external rotation of at least 50% compared to opposite side at 0 degrees of abduction and with normal X ray findings ]. Patients will be included if symptoms present for at least 3 months (Cyriax, 1993; Griggs et al., 2000).

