**Exclusion Criteria**

Severe degeneration, or trauma involving the shoulder (ie, rheumatoid arthritis, osteoarthritis, history of injury to the labrum or articular cartilage or malignancies in the shoulder region, etc.).

Neurologic diseases such as stroke or peripheral nerve neuropathy.

Pain or disorders of the cervical spine, elbow, wrist, or hand.

Pregnancy, cardiac, respiratory, kidney, or circulatory problems pregnancy.

History of fractures, treatment, or surgery to the lumbar spine, thoracic spine, cervical spine, and upper limbs

Injection with corticosteroids in the affected shoulder in the preceding 4 weeks.

Subjects with diabetes mellitus will be accepted.

Inflammatory joint disease affecting the shoulder.

Bilateral frozen shoulder due to possible underlying systemic cause.

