**Outcome Measures**

The primary outcome measure is shoulder range of motion (active and passive shoulder abduction, and active and passive shoulder external rotation) measured by smartphone inclinometer (clinometer plaincode). The secondary outcome measures will be functional outcome measures [measured by the quick Disabilities of the Arm, Shoulder and Hand (Quick DASH) questionnaire and pain [measured using a visual analogue scale (VAS)] and SF-12 and Oxford Shoulder Score (OSS).

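### Entry requires assessing the opposite shoulder's passive external rotation, but the fixed one-way ANOVA uses neither that value nor the affected side's baseline, so precision on external rotation is given away

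*Protocol*

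**What the plan says.** Under Inclusion Criteria, disease must be unilateral, "with loss of passive external rotation of at least 50% compared to opposite side at 0 degrees of abduction". Exclusion Criteria rules out "Bilateral frozen shoulder due to possible underlying systemic cause". Every participant therefore has an unaffected shoulder that was compared with the affected one before randomisation.

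The Intervention section sets the visits: "Subjects will be assessed at baseline and at 3, 6, and 12 months". It also fixes the method for range of motion: "Shoulder external rotation and abduction ROM will be measured and compared within and between groups and will be analyzed using a One-way ANOVA". Data analysis extends that method to everything: "All outcome measures will be analyzed using one-way ANOVA". Neither section names a covariate, and neither says whether the values analysed are follow-up angles or changes.

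The Sample size section makes external rotation the outcome on which the trial is sized: "Shoulder external rotation range of motion is considered as the primary outcome measure for the proposed study". Outcome Measures lists four components, active and passive, for abduction and external rotation.

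**The concern.** The entry rule treats the opposite shoulder as the patient's own normal. If a frozen shoulder recovers towards that normal, people with a naturally large range will tend to end higher than people with a small one, whichever arm they are in. A one-way ANOVA leaves this person-to-person difference in the error term. The same holds for differences in the affected shoulder's range at baseline.

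The opposite-side value is fixed before treatment and cannot be changed by it, so it is a legitimate covariate. With about 30 evaluable patients per arm, allocated by simple envelope randomisation, a chance imbalance in normal range is also quite possible, and adjustment would correct for it. At stake is the width of the confidence interval for external rotation. If the angle is not written down at screening, it may be unavailable later as a pre-randomisation value.

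**Working it through.** **1. The plan's own figure.** The Sample size section gives 22 (12.5) and 33 (14.9) degrees.

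- Pooled SD = √((12.5² + 14.9²)/2) = √189.13 = 13.75 degrees.
- Effect size = 11/13.75 = 0.80 (the protocol gives 0.799 in absolute value).
- Two-sided α 0.05, power 85%, two-sample t-test: 29.06, rounded up to 30 per group. This reproduces the protocol.
- Power without any covariate: 86.1% at 30 per group and 91.0% at 35.

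**2. What one covariate is worth.** If the covariate correlates r with follow-up external rotation, the residual variance falls by the fraction r². The 95% half-width at 30 per group is 1.96 × 13.75 × √(2/30) × √(1 − r²). The protocol gives no r, so a range is shown.

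| r (assumed) | Variance removed | Half-width, degrees | Power at 30 per group |
|---|---|---|---|
| 0 | 0% | 6.96 | 86.1% |
| 0.2 | 4% | 6.82 | 87.5% |
| 0.3 | 9% | 6.64 | 89.1% |
| 0.5 | 25% | 6.03 | 94.0% |
| 0.6 | 36% | 5.57 | 96.8% |

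**3. What the opposite side adds once baseline is in the model.** This needs a model of recovery, and all of its inputs are assumptions:

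- opposite side: mean 65 degrees, SD 8, 12 or 16;
- affected shoulder at entry: 10–50% of the opposite side, in line with the entry rule;
- follow-up = baseline + recovery fraction × (opposite − baseline);
- mean recovery fraction: 25%, 45% and 70% at 3, 6 and 12 months, beta-distributed with between-patient SD 0.15 to 0.25;
- reading error: 5 degrees on every measurement.

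Further reduction in residual variance beyond baseline adjustment (simulated; values move by about one percentage point between runs):

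| Recovery SD | Opposite-side SD | SD of external rotation at 3 months | 3 months | 6 months | 12 months |
|---|---|---|---|---|---|
| 0.15 | 8 | 11.0 | 5% | 11% | 21% |
| 0.15 | 12 | 11.8 | 11% | 23% | 39% |
| 0.15 | 16 | 12.9 | 17% | 34% | 51% |
| 0.20 | 16 | 14.4 | 12% | 26% | 43% |
| 0.25 | 8 | 14.4 | 2% | 6% | 12% |
| 0.25 | 12 | 15.1 | 6% | 13% | 24% |
| 0.25 | 16 | 16.0 | 9% | 20% | 35% |

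**4. Check against the protocol.** Read as a 12-week value, the protocol's SD is 14.9 degrees. A recovery SD of 0.15 gives only 11.0–12.9 degrees at 3 months, so the rows with the largest gains fit least well. A recovery SD of 0.25 comes closer and gives 2–9%, 6–20% and 12–35%.

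**5. Effect on the interval.** The interval shrinks by 1 − √(1 − v), where v is the variance removed.

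- 3 months, v = 2–17%: 1–9% narrower.
- 6 months, v = 6–34%: 3–19% narrower.
- 12 months, v = 12–51%: 6–30% narrower.

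**6. Slower recovery.** The Introduction gives a mean disease duration of 30 months. With mean recovery of 20%, 30% and 40%, and recovery SD 0.15–0.20, the gains are 3–15%, 5–21% and 7–30%. They remain positive and still rise with time, but the 12-month figure is clearly smaller.

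**7. Baseline for comparison.** At 3 months, with recovery SD 0.15, the affected-side baseline alone removes about 26–37% of the variance. The opposite side then adds 5–17%. At that visit the missing baseline is the larger gap.

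**The case against.** The strongest reply is that nothing is wrong in the sense of invalid. Randomisation keeps the unadjusted comparison unbiased, the sample size reproduces without a covariate, and choosing prognostic covariates is partly a matter of preference. All of that stands. It makes this an improvement and not an error. It does not dispose of the point, because the protocol has not left the method open for a later analysis plan: it names one-way ANOVA for every outcome.

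Several narrower objections also stand.

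- No section says that the opposite side sets a ceiling for recovery. A reader might infer this from the entry rule, but the rule only defines the disease.
- A reader might also take it as established that the loss is greatest at 12 months. The ordering follows from the recovery model, provided that shoulders keep improving. The protocol gives no figure for it, and a mean duration of 30 months means that many patients may still be well short of their normal range by then.
- The entry measure is passive external rotation at 0 degrees of abduction. It bears on external rotation and not directly on the abduction components of the primary outcome.
- The rule requires a comparison, but the protocol does not say that the opposite-side angle is recorded in degrees.
- If the ANOVA were run on changes, baseline would enter by subtraction. The opposite-side value would still be unused.
- Baseline and opposite side overlap. In the simulation with opposite-side SD 16 they correlate at about 0.46, so the baseline already carries part of the information.

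**Conclusion.** The point holds as a cheap improvement in precision. The entry rule makes the opposite-side assessment unavoidable before randomisation, and the stated analysis uses neither it nor the affected side's baseline as a covariate. The cost is a wider interval for external rotation. There is no bias, and the stated power is not missed.

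The size cannot be fixed from the protocol. Under the assumptions listed, the opposite side removes a further 2–17%, 6–34% and 12–51% of residual variance at 3, 6 and 12 months beyond baseline. The lower part of each range sits better with the protocol's SD of 14.9 degrees. That comparison itself relies on reading 14.9 as the spread of 12-week angles in a similar population, although the protocol's wording refers to changes. If recovery is slower than assumed, the 12-month gain could be as low as about 7%. If the opposite side does not predict recovery at all, the gain is nil.

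A reader might convert the gain into about seven patients per arm, since 30/(1 − 0.20) = 37.5. That is not supported: the trial is sized on 12-week data, and a 20% further reduction lies outside the 2–17% range for 3 months.

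**What to change.** - At screening, record passive external rotation of the opposite shoulder as a number of degrees, not only whether the entry rule is met.
- For external rotation, replace the one-way ANOVA with a prespecified ANCOVA at each visit, or a mixed model over 3, 6 and 12 months, with the affected-side baseline and the opposite-side value as covariates. In a mixed model, let both slopes differ by visit, since the relation to the opposite side is expected to change as shoulders recover.
- Keep degrees as the outcome scale.
- Make no claim of a smaller sample size on this account.

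The opposite-side value costs one recorded field from an assessment that entry already requires, a sentence in Data analysis (with Intervention amended to match), and one extra degree of freedom in each visit's model. Treatment and eligibility do not change.
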